plus CHX) oral care interventions on development of VAP in critically ill mechanically ventilated adults. A between-subjects 2X2 factorial design was used; 547 subjects were randomly assigned to 1 of 4 treatments: 0.12% solution CHX oral swab twice daily, toothbrushing three times daily, both toothbrushing and CHX, or control (usual care). Oral care interventions were provided by study personnel. Dental plaque was scored on study days 1, 3, 5 and 7 using a standardized scale, the University of Mississippi Oral Hygiene Index (UM-OHI), with observations augmented by use of a dental plaque disclosing agent, visible only under ultra-violet (UV) light so that study personnel providing interventions and clinical providers were not aware of plaque assessment results. Plaque assessors were blinded to subject group assignment. Subjects remained in the study for a maximum of 7 days; participation ended with extubation. Subjects were 61% male, with a mean age of 47.9 years and mean APACHE III score of 77. Serial dental plaque data from admission to the study through day 3 were available for 222 subjects. Mixed model analysis of variance showed a significant effect on dental plaque of the toothbrushing intervention ( $p=0.0411$ ). The CHX intervention had no effect on the presence of dental plaque ( $p=0.9397$ ), and there was no interaction effect between toothbrushing and CHX.

In contrast, when we tested the effects of the interventions on VAP risk as measured by the Clinical Pulmonary Infection Score (CPIS), CHX significantly reduced the incidence of pneumonia on day 3 (CPIS  $\geq 6$ ) among patients who had CPIS  $< 6$  at baseline ( $P = .006$ ), while tooth brushing had no effect on CPIS ( $p = .54$ ) and did not enhance the effect of CHX. We reasoned that although both CHX and tooth brushing reduce organisms in dental plaque, CHX has bacteriocidal activity while tooth brushing mechanically reduces the number of organisms without residual activity on those remaining in the mouth. Thus, dental plaque remained physically present on the teeth of patients who received CHX, but organisms present in the plaque were inhibited. Although tooth brushing physically removed dental plaque, the intermittent reduction in organism numbers achieved by tooth brushing was insufficient to reduce risk of VAP.

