**4. Dental Plaque Accumulation in Mechanically Ventilated Adults.** In a sub-study of this R01 during its initial funding period, dental plaque data was evaluated longitudinally in a subset of the control group enrolled within 24 hours of intubation in the first year of data collection of R01 NR007652 (n=137). Subjects in the control group received usual oral care delivered by the bedside nurse; nurses were free to individualize the method of oral care, and the study units did not have protocols that specified tools and solutions for oral care. Baseline oral health status was assessed by a count of decayed, missing, and filled teeth (DMFT). Dental plaque was assessed using the UM-OHI on study days 1, 3, 5 and 7; observations were augmented by use of a dental plaque disclosing agent, visible only under ultra-violet (UV) light. This dental plaque assessment strategy was substantially more valid and reliable than our previous VAS. On the day of intubation, subjects had greater than 73% mean dental plaque coverage of tooth surfaces, and mean dental plaque remained greater than 60% through day 7, with statistical differences only between day 1 and day 7 ( $p = .03$ ). We further examined the pattern of dental plaque accumulation by location (buccal or lingual) and by tooth type (molars, premolars, canines, incisors). Dental plaque averages for the buccal (67%) and lingual (68%) surfaces were equivalent. The molars and premolar tooth types had the most dental plaque (greater than 70%) when compared to the other tooth types. These data reinforced earlier preliminary results regarding preexisting oral problems in mechanically ventilated adults, and further quantified high levels of dental plaque and DMFT scores. Further, the data indicated that usual oral care provided by bedside nurses was not effective in plaque removal.

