**Statistical Power and Sample Size Justification.** As described above, our primary aim is to evaluate whether a single daily tooth brushing regimen is clinically non-inferior (defined as an effect size of  $\leq 0.50$ ) to a regimen of brushing twice or 3 times daily. The test is considered one-sided as there is no known or postulated biological mechanism to expect a better clinical result (lower plaque score) with the once daily brushing regimen, while at the same time, no reason to expect a higher risk of serious adverse events with this regimen as compared to 3 times daily brushing. To be conservative, we assume that up to 40% of subjects enrolled will have missing data or not provide analyzable data due to intubation for less than 48 hours or less than 2 days follow-up measurement of dental plaque and mucosal inflammation after intubation; this is consistent with our previous and current projects. The non-inferiority trial is powered based on conventional guidelines of type I error rate ( $\alpha$ ) of 0.10 and 95% desired power, and specifying a 1-tailed tolerance limit for non-inferiority as an effect size of 0.50. With these conditions, a sample size of 69 subjects per group (i.e. testing group 1 versus 3) is required. This group size will also be sufficient if the non-inferiority test is not supported, and a secondary test of the 1 versus 2 times daily brushing regimens is necessary. For 3 groups, the required effective sample size is 207 (69 x 3 groups), which taking into account missing and non-usable outcome data results in a proposed total sample size of 345 subjects (i.e. 207 / 0.60). For specific aim #2, it is difficult to estimate the expected proportion of HAs to occur in the respective treatment arms, particularly given the recent change in Centers for Disease Control and Prevention (CDC) National Healthcare Safety Network (NHSN) surveillance definitions for ventilator associated complications, including VAP. If the proportion of subjects who experience HAI within one of the treatment groups ( $n=69$ ) is 0.05, the corresponding 95% confidence interval would be 0.01 to 0.13, indicating reasonable precision.

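### The 40% loss allowance is called conservative and in line with earlier projects, but no count in the document supports it, and the stated 95% power depends on it

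*Combined protocol and SAP*

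**What the plan says.** All references are to the combined protocol and SAP.

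- **Section XI, Statistical Power and Sample Size Justification.** The design needs 69 evaluable subjects per group, from one-sided alpha 0.10, 95% power and a margin of 0.50 in effect-size units. Three groups make 207, and 207/0.60 gives 345. On the 0.60 the text says "To be conservative, we assume that up to 40% of subjects enrolled will have missing data or not provide analyzable data", and then "this is consistent with our previous and current projects". No count follows.
- **Section XI, Specific Aim 1.** The non-inferiority analysis uses subjects with at least 2 days of ventilation and at least 2 days of assigned brushing. The decision rests on a 95% confidence interval.
- **Section VIII, Preliminary Studies, study 1 (the initial trial).** "547 subjects were randomly assigned to 1 of 4 treatments". "Serial dental plaque data from admission to the study through day 3 were available for 222 subjects". The schedule was sparser than the one planned now: "Dental plaque was scored on study days 1, 3, 5 and 7 using a standardized scale".
- **Section VIII, Progress Report (the current project).** 314 subjects were enrolled, and 94 (47 per group) had the complete pneumonia-score (CPIS) data needed for the repeated-measures analysis.
- **Section IX, Intervention.** 229 subjects of the initial trial are said to have been assigned to brushing.

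**The concern.** The allowance is the only step between 69 evaluable subjects per arm and 345 enrolled. The reader is told that it is cautious and backed by experience. Yet the two completeness figures that the document prints for those same projects both show more than 40% missing, and no section shows 40% or less.

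Because 345 is exactly 207/0.60, the enrolment figure holds no reserve beyond the allowance. Each further percentage point of loss removes 1.15 evaluable subjects per arm (345 × 0.01 / 3). Lost power also reaches the trial's conclusion: in Table 2, failure to support non-inferiority is read as once-daily brushing being inferior, and with a number needed to harm of 100 or more it leads to the three-times-daily recommendation.

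**Working it through.** **1. The plan's own figures.** With margin 0.50 SD, true difference 0, one-sided alpha 0.10 and power 0.95:

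n per arm = 2(1.2816 + 1.6449)² / 0.50² = 8 × 8.564 = 68.5, so 69. Then 3 × 69 = 207, and 207/0.60 = 345. All three reproduce.

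**2. What the document shows about loss.**

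- Initial trial, plaque on the same index: 222/547 = 40.6% available, 59.4% without. The exact 95% interval for availability is 36.4% to 44.8%.
- Current project, not plaque: 94/314 = 29.9% included, 70.1% not included.
- For 40% loss to have held in the initial trial under the new rule, 329 of 547 would have to be evaluable (0.60 × 547 = 328.2). That is 107 more than 222, or 33% of the 325 without serial data (107/325). The document neither shows nor excludes this.

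**3. Caveat on the denominator.** Two of four equal arms of 547 would hold about 274 subjects, not 229. If 229 were two of four equal arms, the total would be about 458. Availability would then be 222/458 = 48.5%, a loss of 51.5%. Equal arms and the total of 458 are assumptions.

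**4. Power with 345 enrolled.** Evaluable per arm = 345 × (1 − loss)/3. Power = Φ(0.50 × √(n/2) − z), with z = 1.2816 (one-sided alpha 0.10), 1.6449 (one-sided 95% bound) or 1.9600 (two-sided 95% interval).

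| Loss | Evaluable per arm | One-sided alpha 0.10 | One-sided 95% bound | Two-sided 95% interval |
|---|---|---|---|---|
| 40% (plan) | 69 | 95% | 90% | 84% |
| 50% | 57.5 | 92% | 85% | 76% |
| 51.5% (222 of an assumed 458) | 55.7 | 91% | 84% | 75% |
| 59.4% (222 of 547) | 46.7 | 87% | 78% | 68% |
| 60% | 46 | 87% | 77% | 67% |

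Example at 60%: 0.50 × √(46/2) = 2.398; 2.398 − 1.2816 = 1.116, and Φ(1.116) = 0.868. Using the t distribution changes the 40% and 60% rows by no more than about one percentage point.

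Power of 80% needs 36.1, 49.5 or 62.8 per arm under the three readings. It is therefore lost once loss passes about 69%, 57% or 45%.

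**The case against.** The strongest reply is that the two counts measure something else, and much of that stands. The initial trial scored plaque every second day, and "Subjects remained in the study for a maximum of 7 days; participation ended with extubation". A subject extubated after 2 days but before a day 3 score would be missing there and could be evaluable here. This trial images daily and requires at least one tooth. The document does not say why 325 subjects lacked serial data. The current project's figure is not plaque at all. The appeal to earlier projects may rest on records that the document does not tabulate, so the claim is undocumented rather than disproved.

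The size of the effect is also open to reply. At the stated alpha, power is still about 87% at 59.4% loss, because a 95% target is itself a cushion. Adjustment for baseline plaque could recover some power: with an assumed baseline correlation of 0.3 to 0.5, and the margin in unadjusted SD units, 46.7 per arm gives about 89% to 93%. And the drop from 95% to 84% at 69 per arm comes from the choice of interval, not from attrition.

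Two arguments that loss should be higher here are tempting but weak.

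- The sample-size section counts "less than 2 days follow-up measurement of dental plaque and mucosal inflammation after intubation" among the reasons for loss, so a reader might infer that a missing IL-1β sample removes a subject. The Aim 1 ANCOVA uses plaque, and its analysis set is defined by days of ventilation and regimen.
- A reader might compare this trial's 36-hour entry window with subjects "enrolled within 24 hours of intubation in the first year of data collection". That phrase describes a control-group subset, not all 547. A later entry also works both ways: it leaves fewer hours to reach 2 days of ventilation, but 2 days of assigned brushing must still follow.

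What the reply does not supply is any figure at or below 40%.

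**Conclusion.** The allowance of 40% is unsupported as printed. The document's figures do not bear out the description of it as conservative, or the statement that it agrees with both earlier projects.

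A reader might go further and infer that the trial will lose 59%, that 69 per arm is out of reach, or that about 511 subjects must be enrolled (207/0.4059 = 510.04). The document does not support that. The proxy follows another schedule and another evaluability rule, and its denominator is not reconciled with the 229.

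The effect is moderate at the stated one-sided alpha of 0.10: about 95% power at 40% loss and 87% at 60%. It is larger if the Aim 1 interval is two-sided: about 84% and 67%. Separately from loss, the 95% interval in Aim 1 does not match alpha 0.10, and 95% power is not delivered under it even at 69 per arm (about 90% for a one-sided bound, 84% for a two-sided interval).

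These figures assume a margin of 0.50 SD, a true difference of 0, equal loss across arms and no gain from baseline adjustment.

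**What to change.** 1. In the sample-size section, delete the description of the allowance as conservative and the claim of agreement with earlier projects. Alternatively, keep them and print the prior-project count under the Aim 1 evaluability rule (at least 2 days ventilated and at least 2 days of regimen).
2. If no such count exists, cite 222 of 547 and say why loss should be lower here (daily scoring, the one-tooth criterion, the 2-day rule). Note that 229 assigned to brushing leaves the 547 to be reconciled.
3. State which interval decides non-inferiority, and give power with 345 enrolled at 40%, 50% and 60% loss for that interval:
   - one-sided alpha 0.10: about 95%, 92% and 87%
   - one-sided 95% bound: about 90%, 85% and 77%
   - two-sided 95% interval: about 84%, 76% and 67%

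The cost is a few sentences. Enrolment, the primary outcome and the ANCOVA are unchanged. The one disadvantage is a less favourable stated power. If the sponsor holds a count that supports 40%, one sentence settles the loss question, and only the choice of interval remains to be stated.

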## **XI. DATA ANALYSIS PLAN**

The data analysis approach for this trial is considered innovative in that it will focus on providing appropriate clinical practice guidelines through testing of non-inferiority and quantification of number needed to harm, as opposed to conventional testing of superiority among respective randomly-assigned treatment regimens. Specifically, we will first evaluate whether the single tooth brushing regimen is clinically equivalent (non-inferior) to brushing two or 3 times daily, and also quantify the respective risk versus clinical benefit of brushing multiple times daily. The sample size and power analyses (see below) are based principally on specific aim #1 and a one-sided test of non-inferiority for the once daily tooth brushing regimen.

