Specific Aim 1 is to evaluate the clinical equivalence (non-inferiority) of three tooth brushing frequencies on oral health (dental plaque and mucosal inflammation) in critically ill adults receiving mechanical ventilation. To evaluate non-inferiority, we will use data from subjects who have at least 2 days duration of mechanical ventilation and at least 2 days of their randomly assigned tooth brushing regimen. Recognizing variable length of hospital stay and intubation, we will determine as the primary outcome the maximum difference in dental plaque since baseline assessment at the time of intubation. Whereas we would expect balanced distribution of the specific post-admission day in which this maximum difference is achieved between the 3 treatment arms (e.g. day 4, day 5, etc.), timing of the assessment will be included as a covariate along with baseline dental plaque score. Analysis of covariance (ANCOVA) will be used to compare adjusted dental plaque scores between the 1 and 3 times daily tooth brushing regimens. The test for non-inferiority of the single daily brushing regimen will be based on the 95% confidence interval for the adjusted difference between the 2 groups. For this analysis, we define non-inferiority as a modest between-group effect size of 0.50 or less (i.e. modest to low treatment effect associated with tooth brushing 3 times daily). Thus, if the upper limit of the confidence interval for the effect size is <0.50, then the single daily brushing regimen will be considered non-inferior to the 3 times daily tooth brushing regimen. If the non-inferiority test is not supported, a secondary test of the 1 versus 2 times daily brushing regimens will be conducted. Using this strategy, a direct test of non-inferiority of 2 versus 3 times daily is not required (see Table 2).

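### The 69 per group is sized at one-sided alpha 0.10, but non-inferiority is decided on a 95% confidence interval, so the stated 95% power is about 83 to 84%

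*Combined protocol and SAP*

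**What the plan says.** Section XI (Data Analysis Plan) describes the primary test in two places.

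*Sizing.* The opening paragraph says the sample size rests mainly on Aim 1 and on "a one-sided test of non-inferiority for the once daily tooth brushing regimen". The paragraph on statistical power and sample size repeats this ("The test is considered one-sided as there is no known or postulated biological mechanism") and sets a type I error rate "of 0.10 and 95% desired power, and specifying a 1-tailed tolerance limit for non-inferiority as an effect size of 0.50". From these inputs it concludes that "a sample size of 69 subjects per group (i.e. testing group 1 versus 3) is required". Three groups give 207 evaluable subjects, and allowing for 40% unusable data gives 345 enrolled. The same group size is said to be enough for the fallback comparison of once versus twice daily.

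*Decision.* The Specific Aim 1 paragraph sets the margin ("we define non-inferiority as a modest between-group effect size of 0.50 or less") and says the test "will be based on the 95% confidence interval for the adjusted difference between the 2 groups". Once-daily brushing is declared non-inferior "if the upper limit of the confidence interval for the effect size is <0.50". The interval is not described as one-sided, and no 80% or 90% interval is mentioned.

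**The concern.** A confidence-interval rule carries its own significance level. Requiring the upper limit of a two-sided 95% interval to lie below the margin is a one-sided test at 0.025. The interval that matches one-sided alpha 0.10 is a two-sided 80% interval, which the plan never mentions. The sample size therefore belongs to a more lenient test than the one that will decide the trial.

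Two things are at stake. First, the risk of missing non-inferiority when it is true is larger than stated. Table 2 turns such a miss into practice guidance: every row in which non-inferiority is not supported gives inferiority of once-daily brushing as part of its rationale, and when the number needed to harm is 100 or more the recommendation moves to more frequent brushing. Second, the plan leaves two significance levels on record for one primary test. Some results would pass under one and fail under the other, and that should be settled before any data are seen.

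**Working it through.** **Inputs, all from section XI.** Margin 0.50 in SD units (so SD = 1); equal groups; 69 evaluable per group; one-sided test. The true difference is not stated. I take it as zero, the value that reproduces the plan's 69.

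**Step 1. Reproduce the plan's figure.** The normal-approximation formula is n per group = 2(z_α + z_β)² / 0.50² = 8(z_α + z_β)².

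- One-sided alpha 0.10, power 95%: 8 × (1.2816 + 1.6449)² = 68.5, so 69. A noncentral-t search also gives 69.
- 69 × 3 = 207, and 207 / 0.60 = 345.

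The plan's numbers follow from its stated inputs.

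**Step 2. Power at 69 per group under each reading of the decision rule.** Power = Φ(0.50 × √(69/2) − z_α) = Φ(2.937 − z_α).

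| Decision rule | One-sided alpha | Φ argument | Power (normal) | Power (noncentral t) |
|---|---|---|---|---|
| Two-sided 80% CI (matches the sizing text) | 0.10 | 2.937 − 1.282 = 1.655 | 95.1% | 95.0% |
| One-sided 95% bound | 0.05 | 2.937 − 1.645 = 1.292 | 90.2% | 89.9% |
| Two-sided 95% CI (ordinary reading of Aim 1) | 0.025 | 2.937 − 1.960 = 0.977 | 83.6% | 83.0% |

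Building the two-sided 95% interval directly on the standardised effect size gives 83.4%.

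**Step 3. Sample size for 95% power under the written rule.** 8 × (1.9600 + 1.6449)² = 104.0, so 104 per group: 312 evaluable and 312 / 0.60 = 520 enrolled. By noncentral t it is 105 per group: 315 evaluable and 525 enrolled.

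**Step 4. Results on which the two levels disagree.** With 69 per group the standard error is √(2/69) = 0.170 SD. The upper limit stays below 0.50 when the observed disadvantage of once-daily brushing is below:

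- 0.50 − 1.282 × 0.170 = 0.28 SD for the 80% interval;
- 0.50 − 1.960 × 0.170 = 0.17 SD for the 95% interval.

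Any observed difference between about 0.17 and 0.28 SD passes at the sizing alpha and fails under the Aim 1 rule.

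**Step 5. Sensitivity to a small true disadvantage (an assumption, not in the plan).** If once daily is truly 0.1 SD worse, the first term becomes 0.40 × √(69/2) = 2.349. Power is then Φ(2.349 − 1.960) = 65% under the 95% interval and Φ(2.349 − 1.282) = 86% at alpha 0.10. The assumed difference accounts for the fall from 95% to 86%, and the change of alpha for the fall from 86% to 65%.

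**The case against.** The arithmetic in the plan is not wrong: 69, 207 and 345 all follow from the stated inputs. The fault is an inconsistency between two paragraphs. The other side has four further points.

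*Sidedness.* The plan calls the test one-sided three times, and the rule uses only the upper limit, so a one-sided 95% bound is a possible reading. The formula is symmetric in alpha and beta, so one-sided 0.05 with 90% power also gives 68.5, hence 69. The two values may simply have been transposed. This cannot be excluded. On that reading, however, the sizing sentence misstates both numbers and still needs correcting, and power is about 90%, not 95%.

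*Covariate adjustment.* The analysis is ANCOVA with baseline plaque as a covariate. If the 0.50 is in unadjusted SD units, which the plan does not say, an assumed correlation r divides the first term by √(1 − r²). For r = 0.3 to 0.5, power with the two-sided 95% interval becomes Φ(2.937/0.954 − 1.960) = 87% to Φ(2.937/0.866 − 1.960) = 92%. With a one-sided bound and r = 0.5 it would reach Φ(3.391 − 1.645) = 96%. The plan gives no correlation and claims no such gain, and if the 0.50 is in adjusted SD units there is none.

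*Loss below 40%.* The plan calls 40% conservative. At 30% loss (80 per group) power with the two-sided interval is Φ(0.50 × √40 − 1.960) = 88.5%. At 25% (86 per group) it is Φ(0.50 × √43 − 1.960) = 90.6%. But the plan also says 40% agrees with the team's earlier studies.

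*Consequences.* The rule that will be applied is stricter than the sizing alpha, so a false claim of non-inferiority is not made more likely. In Table 2 a miss does not always change the recommendation, which also depends on the number needed to harm. Both points are right and limit the harm. Neither makes the stated power correct.

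**Conclusion.** The concern holds. At 69 evaluable per group, with a 0.50 SD margin, zero true difference and no credit for covariates, the written decision rule has about 83 to 84% power, not 95%. The chance of missing non-inferiority between equal regimens is about 16 to 17% rather than 5%. If the interval was meant as a one-sided 95% bound, power is about 90% and the chance of a miss about 10%. Neither reading of the 95% interval delivers the stated power on the plan's own inputs, and nothing elsewhere in the document reconciles the two levels. The same gap applies to the once versus twice daily test, which the plan calls adequately powered at this group size.

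This should be corrected before analysis, because it concerns the primary test and leaves the operative alpha open. It does not threaten the validity of a positive non-inferiority finding under the 95% rule.

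**What to change.** Keep the 95% interval rule and the total of 345, and make the two paragraphs agree.

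- In the Specific Aim 1 paragraph, state that the interval is two-sided 95%, equivalent to one-sided alpha 0.025.
- In the power paragraph, delete alpha 0.10 with 95% power. State instead one-sided alpha 0.025 with about 83% power at 69 evaluable per group, margin 0.50 SD and zero true difference. Apply the same figure to the once versus twice daily test.
- If a one-sided 95% bound was intended, say so under Aim 1, and state alpha 0.05 and about 90% power in the power paragraph.

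The choice between the two should be dated before outcome data are seen. The cost is wording and a less favourable stated power, with no extra subjects. Restoring 95% power under the two-sided interval would instead mean 104 per group, or 520 enrolled at 40% loss, which is 175 more than planned.
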